6.5.2 Determination donor specific antibodies (DSAs) and complement fixation

Samples for determination of DSAs will be analyzed in immunoglobulin (Ig) G single antigen solid-phase immunoassay (SA-SPA) for antibodies to HLA class I and class II. The assay allows determination of the mean fluorescence intensity (MFI) of antibodies in patient serum reacting to an array of individual HLA immobilized to beads. In addition, anti-HLA antibodies with complement fixation ability by detection of C1q will be analyzed in a SAB assay. Determination of DSAs will be performed at a central laboratory.

6.6 Clinical safety assessments

6.6.1 Physical examination

For timing of individual examinations refer to the study flow chart 1. A complete physical examination will be performed at screening and day 180 and include an assessment of the following: general appearance, head and neck, lymph nodes, abdomen, musculo-skeletal, cardiovascular, respiratory and gross neurological examination.

6.6.2 Height and weight

Regarding the timing for assessments of height and weight refer to the study flow charts 1 and 2 (Table 1 and Table 2). Measurements should be taken without shoes. Body mass index will be calculated from the height and weight. The timing of individual measurements is indicated in the study flow chart (Table 1 and Table 2).

6.6.3 ECG

ECG 12-lead will be taken after 10 minutes rest at screening and on day 180.

6.6.4 Vital signs

Vital signs, blood pressure, pulse and respiratory frequency will be measured as outlined in the study flow charts 1 and 2 (Table 1 and Table 2). At dosing, blood pressure and pulse will be recorded pre-dose, 2, 6, 24 and 48 hours post-dose. In addition, the patients will be monitored with oximetry during the infusion and the following 24 hours.

6.6.5 Other safety assessments

Body temperature will be measured as specified in the study flow charts at screening and study visit 2 (Table 1 and Table 2). At visit 2/dosing, body temperature will be recorded pre-dose, 2, 6, 24 and 48 hours post-dose.

6.6.6 Kidney biopsy

A kidney biopsy will be performed at visit 2 on deceased donor kidneys and at visit 12 on living and deceased donor kidneys (Table 1). If standard of care kidney biopsies are performed for any reason, e.g. suspected rejections, a de-identified copy of the kidney biopsy report will be collected.

6.7 Laboratory safety assessments

Timing of laboratory efficacy parameters is given in the study flow charts 1 and 2 (Table 1 and Table 2). The date and time of collection will be recorded on the laboratory requisition form and in the CRF. Samples will be labelled, stored and shipped as detailed in the laboratory manual.

6.7.1 Clinical chemistry, hematology, coagulation and virology

The following blood samples for determination of clinical chemistry, hematology, coagulation and total IgG in plasma will be taken:

Table 5. Clinical chemistry, hematology, coagulation and virology

P-IgG, total	P-PK(INR)
P-ALP	P-APTt
P-ALT	Hematology
P-AST	B-Hemoglobin
P-Bilirubin, total	B-Differential analysis of leucocytes
P-Glucose	B-Thrombocytes

P-Sodium

P-CRP

***Virology**

P-Albumin

B-HIV

P-Urea

B-Hepatitis B surface antigen

P-Triglycerides

B-Hepatitis C antibodies

P-Creatinine

P-Creatinine
phosphokinase

*Virology samples for HIV and hepatitis will be taken at screening. Test results not older than 6 months can be used.

Additional laboratory variables can be performed if judged appropriate by the investigator.

6.7.2 Viral surveillance

Samples will be taken in all patients as outlined in the study flow chart for BK-, EBV and CMV-PCR for early diagnosis of viral activations/reactivations and early treatment, respectively. Extra samples should be taken if indicated. At screening, results not older than 6 months can be used.

6.7.3 Pregnancy test

Serum B-HCG will be determined at screening, pre-dose and on day 180 using validated standard methods

6.7.4 Determination of kidney function

Evaluation of kidney function will be done based on P-creatinine analysis and calculation of filtration rate (eGFR). Proteinuria tests (spot urine/creatinine) will be performed at the time points indicated in the study flowcharts. In addition 24 hour urine collections for electrophoresis analysis of proteins will be performed daily starting after transplantation and up to day 9. The amount of urine per 24 hour will be measured and two samples will be taken from the collection. One sample will be analyzed at the hospital laboratory and one sample will be stored and analyzed later if deemed necessary.

6.8 Pharmacokinetics and pharmacodynamics

6.8.1 Determination of drug concentration in biological samples

Samples for determination of IdeS levels in serum (PK) will be performed at the time points indicated in the study flowcharts and analyzed by [REDACTED]

6.8.2 Determination of IgG levels in serum

Samples for determination of IgG levels in serum (PD) will be performed at the time points indicated in the study flowcharts and analyzed by [REDACTED],

England. Samples will also be qualitatively analyzed by gel electrophoresis for IgG integrity by [REDACTED]

6.9 Anti-drug antibody analysis

Venous blood samples for determination of anti-drug antibodies (ADA) will be taken at the times presented in the study flow charts ([Table 1](#) and [Table 2](#)) and analyzed by [REDACTED]. Determination of anti-IdeS IgG antibody concentrations in serum will be performed using anti-IdeS ImmunoCAP. At screening anti-IdeS IgE antibodies will be drawn. This will be used for research purpose for patients with deceased donors and as part of the eligibility criteria for patients with live donors.

The normal range of anti-IdeS IgG antibodies is <2-78 mg/L ([HMed Doc. No. 2012-041](#)). Patients who are not back within the normal ADA range at study completion will be asked to come back for a follow up ADA sampling at 12 months. The results from the 12 months ADA samples will be reported separately.

7 Biological sampling procedures

7.1 Handling, storage and destruction of biological samples

Samples will be used or disposed after analyses. A detailed description on sample collection, handling and shipping will be provided in a separate laboratory manual.

7.1.1 Pharmacokinetic, pharmacodynamic and anti-drug antibody samples

Samples will be disposed after the clinical study report has been finalized, unless retained. [REDACTED] Study samples may be stored on behalf of the sponsor for a maximum of four years after completion of the study report.

7.2 Chain of custody of biological samples

A full chain of custody is maintained for all samples throughout their life cycle.

The principal investigator keeps full traceability of collected biological samples from the patients while in storage at the center until shipment and keeps documentation of receipt of arrival.

The sample receiver keeps full traceability of the samples while in storage and during use until used or disposed.

Sponsor keeps oversight of the entire life cycle through internal procedures, monitoring of study sites and auditing of external laboratory providers.

7.3 Withdrawal of informed consent for donated biological samples

If a patient withdraws consent to the use of biological samples donated the samples will be disposed/destroyed, if not already analyzed and documented.

The principal investigator:

- will ensure that patient withdrawal of informed consent is notified immediately to sponsor
- will ensure that biological samples from that patient, if stored at the study site, are immediately identified, disposed/destroyed and the action documented.
- will ensure the laboratory(ies) holding the samples is/are informed about the withdrawn consent immediately and that samples are disposed/destroyed and the action documented returned to the study site.

In the event that analysis/research has already been performed, sponsor will retain the results and associated data for regulatory reasons but these will not be used in any subsequent analyses.

8 Ethical and regulatory requirements

8.1 Ethical conduct of the study

The study will be performed in accordance with ethical principles that have their origin in the latest Declaration of Helsinki and are consistent with ICH/Good Clinical Practice, applicable regulatory requirements.

8.2 Patient data protection

The informed consent form (ICF) will incorporate wording that complies with relevant data protection and privacy legislation.

8.3 Ethics and regulatory review

An ethical review board must approve the final study protocol, including the final version of the ICF and any other written information to be provided to the patients. The investigator will ensure the distribution of these documents to the applicable ethical review board, and to the study site staff. The opinion of the ethical review board must be given in writing.

Sponsor must approve any modifications to the ICF that are needed to meet local requirements.

No patient will be enrolled in the study, the final study protocol, and the final version of the informed consent form are approved by the national regulatory authority or a notification to the national regulatory authority is done, according to local regulations.

The distribution of any of these documents to the national regulatory authorities will be handled by sponsor.

Sponsor will provide ethical review boards and principal investigators with safety updates/reports according to local requirements.

Progress reports and notifications of serious and unexpected adverse drug reactions will be provided to the ethical review board according to local regulations and guidelines.

8.4 Informed consent

The principal investigator(s) at the centers will:

- Ensure that the patient is given full and adequate oral and written/read information about the nature, purpose, possible risk and benefit of the study.
- Ensure that the patients are notified that they are free to discontinue the study at any time.
- Ensure that the patient is given the opportunity to ask questions and allowed time to consider the information provided.
- Obtain and document the patient's signed and dated informed consent before conducting any procedure specifically for the study.
- Ensure the original, signed informed consent form is stored in the Investigator's Study File.
- Ensure a copy of the signed informed consent form is given to the patient.

8.5 Changes to the protocol and informed consent form

Study procedures will not be changed without the mutual agreement of the principal investigator and sponsor.

If there are any changes to the study protocol, then these changes will be documented in a study protocol amendment.

The substantial amendment(s) must be submitted to regulatory authorities and approved by the ethical review board before implementation. Local requirements must be followed for amended protocols and approval obtained if required. Sponsor will distribute any subsequent amendments and new versions of the protocol to the principal investigator.

If a protocol amendment requires a change to a center's informed consent form, sponsor and the center's ethical review board must approve the revised informed consent form before the revised form is used.

If local regulations require, any administrative change will be communicated to or approved by the ethical review board.

8.6 Audits and inspections

The investigator(s)/institution will permit study-related monitoring, audits, IRB/IEC review, a regulatory inspection(s), providing direct access to source data/documents and give permission to examine, analyze, verify, and reproduce any records and reports that are important to evaluation of a clinical study. Any party (e.g., domestic and foreign regulatory authorities, sponsor's monitors and auditors) with direct access should take all reasonable precautions within the constraints of the applicable regulatory requirements(s) to maintain the confidentiality of patients' identities and sponsor's proprietary information.

Authorized representatives of sponsor or a regulatory authority may perform audits or inspections at the center, including source data verification. The purpose of an audit or inspection is to systematically and independently examine all study-related activities and documents, to determine whether these activities were conducted, and data were recorded, analyzed, and accurately reported according to the protocol, Good Clinical Practice (GCP), guidelines of the International Conference on Harmonization (ICH), and any applicable regulatory requirements. The investigator will contact sponsor immediately if contacted by a regulatory agency about an inspection at the center.

8.7 Archiving of Investigator Study File and Study Master File

The investigator is responsible for maintaining all records, which enable the conduct of the study at the site to be fully understood, in compliance with ICH-GCP. The study documentation including all the relevant correspondence should be kept by the investigator for at least 10 years after the study report is final. No study documents may be destroyed without prior written agreement between the investigator and Hansa Medical AB. Should the investigator elect to assign the study documents to another party, or move them to another location, Hansa Medical AB must be notified.

Hansa Medical AB will archive the Study Master File in accordance with ICH-GCP and applicable regulatory requirements.

9 Study management

9.1 Pre-study activities

Before the first patient is entered into the study, it is necessary for a representative of sponsor to visit the investigational study site for a site initiation visit to:

- Determine the adequacy of the facilities to give the sponsor information about whether the study centre has knowledge, enough time, a sufficient patient pool, and sufficient training to manage the study in a good way in terms of patient inclusion, patient handling, data and overall study management.
- Discuss with the investigator(s) (and other personnel involved with the study) their responsibilities with regard to protocol adherence and the responsibilities of sponsor or its representatives. This will be documented in a site initiation visit report and in the clinical study agreement between sponsor and the investigator

Before the first patient is entered into the study, a sponsor representative will review and discuss the requirements of the clinical study protocol and related documents with the investigational staff and also train them in any study specific procedures and system(s) utilised.

The principal investigator will ensure that appropriate training relevant to the study is given to all staff, and that any new information relevant to the performance of this study is forwarded to the staff involved.

The principal investigator will maintain a record of all individuals involved in the study (medical, nursing and other staff).

9.2 Monitoring of the study

During the study, a sponsor representative will have regular contacts with the study site, including visits to:

- Provide information and support to the investigator(s).
- Confirm that facilities remain acceptable.
- Confirm that the investigational team is adhering to the protocol, data are being accurately and timely recorded in the CRFs, and investigational product accountability checks are being performed.
- Perform source data verification (a comparison of the data in the CRFs with the patient's medical records at the hospital or practice, and other records relevant to the study) including verification of informed consent of participating patients. This will be done using print outs of records for each patient.
- Ensure withdrawal of informed consent to the use of the patient's biological samples is reported and biological samples are identified and disposed/destroyed accordingly, and the action is documented, and reported to the patient.

The sponsor and the CRO will be available between visits if the investigator(s) or other staff at the center needs information and advice about the study conduct.

9.3 Source data

Refer to the source data document for location of source data.

9.4 Study agreements

The principal investigator must comply with all the terms, conditions, and obligations of the clinical study agreement for this study. In the event of any inconsistency between this clinical study protocol and the clinical study agreement, the clinical study protocol will prevail.

Agreements between sponsor and the principal investigator must be in place before any study-related procedures can take place, or patients be enrolled.

9.5 Insurance

All patients in the study are covered by an insurance held by Hansa Medical AB.

9.6 End of study

The end of the study is defined as "the last visit of the last patient".

10 Data handling

10.1 Case Report Forms

A CRF/eCRF will be provided by a CRO. If an eCRF is chosen the system should be validated in accordance with regulatory and system requirements.

10.2 Source data

The source data document will provide information on the location of source data.

10.3 Data management

[figure not shown]
All data management procedures will be outsourced to a CRO [REDACTED]. Activities will be specified in a Data management Plan prepared by the CRO and reviewed and approved by the Sponsor. The plan will be issued before data collection begins and will describe all functions, processes and specifications for data collection, cleaning and validation.

For medical coding of AEs, medical history and concomitant medication the most recent versions of MedDRA and WHO Drug will be used. The coding will be outsourced to a third party. When all data has been processed, queries resolved, medical coding completed and any issues from review of protocol violations and data listings resolved, the data base will be locked and any further update will be denied.

11 Evaluation and calculation of pharmacokinetic and pharmacodynamics variables

11.1 Calculation or derivation of pharmacokinetic variables

Pharmacokinetic analysis of the serum concentration data for IdeS will be performed at the appointed CRO on behalf of sponsor. The actual sampling times will be used in the parameter calculations. Concentration-time raw data and pharmacokinetic parameters will be calculated for each individual as well as reported per received dose(s).

[REDACTED] the area under the curve to infinite time (AUC), the terminal half-life ($T_{1/2}$), clearance (CL), volume of distribution at steady-state (V_{ss}) and volume of distribution during the elimination phase (V_z). In addition the maximum plasma concentration (C_{max}) and the time of occurrence of C_{max} (T_{max}) may be obtained directly from the experimental data.

12 Statistical methods and sample size

Prior to clean file a Statistical Analysis Plan (SAP) with details on statistical analysis and data presentation will be written.

12.1 Description of analysis sets

The safety analysis set will consist of all patients that received any amount of study medication.

The Full Analysis Set (FAS) will consist of all patients in the safety set that has a measurement of anti-HLA antibody level within 24 hours from dosing.

The Per Protocol Set (PPS) will be defined by the PK analyst.

The final criteria for the PPS, regarding which protocol deviations that warrant exclusions, will be determined when all data on protocol violations/deviations are available.

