12.2 Methods of statistical analyses

12.2.1 General principles

No formal statistical hypothesis testing will be performed in this study. Data will be presented by actual dose received.

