12.3 Determination of sample size

Sample size is not based on formal statistical considerations. Due to the nature of the primary endpoint of the study it is expected that data from 15-20 patients should suffice to achieve the objectives of the study. Also, the sample size is in line with experience from previous similar Phase II studies with other compounds to obtain adequate safety, tolerability and PK data to achieve the objectives of the study.

13 Publication policy

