### **3 Analysis sets**

The analysis sets will be determined at the data review prior to database lock. Decisions will be documented in the database lock minutes.

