## **4.4 Efficacy**

### **4.4.1 Primary efficacy analysis**

The primary efficacy endpoint is defined as imlifidase ability to create a negative crossmatch test within 24 hours after imlifidase dosing. The primary endpoint will be presented for the PP analysis sets.

The planned time points (according to the flowchart) are: Screening, pre-dose, 2h, 6h, 24h, and 48h. In general, only the pre-dose and 24h analyses are performed, while the other planned analyses are missing. For each of the crossmatch tests (FACS B-cell, FACS T-cell, amplified and non-amplified analyses of CDC B-cells and CDC T-cells, and virtual) summary tabulations by time point will be made.

For each patient an overall response is defined as positive if at least one of the assays is positive at pre-dose and all recorded assays are negative at 24h. The overall response is summary tabulated.

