## 5 Deviations from protocol analysis

The protocol stated that PK analysis of the serum concentration data for imlifidase would be performed at the appointed CRO on behalf of sponsor, but it will be performed by the Hansa Medical responsible pharmacokineticist.

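### The only set used for the primary efficacy result excludes undefined 'major' violations graded after the open-label crossmatch outcome is known, and no efficacy display covers all treated patients

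*Protocol*

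**What the plan says.** **Timing.** The opening of protocol section 12 sets the deadline for the SAP: "Prior to clean file a Statistical Analysis Plan (SAP) with details on statistical analysis and data presentation will be written". Protocol 12.1 leaves the final exclusion criteria for the per-protocol set (PPS) open: "regarding which protocol deviations that warrant exclusions, will be determined when all data on protocol violations/deviations are available". SAP 3 keeps this order: "The analysis sets will be determined at the data review prior to database lock". It adds that decisions go into the database lock minutes.

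**Rule.** SAP 3.2 admits to PP any patient in the safety set with at least one recorded efficacy value, then removes those with one or more major violations. It does not list or define what counts as major, and neither does the protocol.

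**Use.** SAP 4.4.1: "The primary endpoint will be presented for the PP analysis sets". SAP 4.4.2 does the same for secondary efficacy. Protocol 12.1 also defines a full analysis set (FAS): treated patients with an anti-HLA antibody measurement within 24 hours. The SAP has only a safety set and a PP set, and SAP 5 does not mention that the FAS is gone.

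**Who decides.** Protocol 12.1: "The Per Protocol Set (PPS) will be defined by the PK analyst". The SAP does not repeat this and names no one in its place.

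**The concern.** The primary result is a single proportion in one arm. Who is in the denominator therefore matters as much as who responds, and no control arm exists in which selective exclusions might balance out.

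The response is read within 24 hours. Under protocol 4.1 a crossmatch that stays positive opens the option of a second dose, and patients who do not become eligible are not transplanted. Protocol 4.2 also has the crossmatch results of the first three patients evaluated for the escalation decision. The outcome is thus known well before anyone grades a deviation, and neither document asks that the grading be done without it.

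Under these rules the same deviation could be graded major in a non-converter and minor in a converter without breaching the plan. At stake is the point estimate and its reading, for example whether the report says that all patients converted or that nearly all did.

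**Working it through.** **Step 1. Is there a planned figure to reproduce?** No. Protocol 12.3: "Sample size is not based on formal statistical considerations". The documents give 15 to 20 patients but no assumed response rate, power or precision target. SAP 4.1 plans counts and percentages and mentions no confidence interval.

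**Step 2. Set the passages side by side.**
- Exclusion criterion: major violation, undefined (SAP 3.2).
- When it is settled: once all deviations are known (protocol 12.1), at the data review (SAP 3).
- What is known by then: the 24 h crossmatch, in an open-label study (SAP 2.3; protocol 3.3 and 4.1).
- Another efficacy set to compare with: none (SAP 3, 4.4.1, 4.4.2).

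**Step 3. Size of the effect.** Assumptions, not in the documents: n = 15, 18 or 20 treated, with 1, 2 or 3 non-responders. Let x be the number of responders.
- Remove one non-responder: x/(n−1) − x/n = x/[n(n−1)].
- Remove one responder: x/n − (x−1)/(n−1) = (n−x)/[n(n−1)].

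Example, n = 15 and x = 14: the gain is 14/210 = 6.7 points and the loss is 1/210 = 0.5 points. Example, n = 20 and x = 17: the gain is 17/380 = 4.5 points and the loss is 3/380 = 0.8 points.

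| All treated (exact 95% CI) | One non-responder removed (exact 95% CI) | Gain, points | One responder removed | Loss, points |
|---|---|---|---|---|
| 14/15 = 93.3% (68.1–99.8) | 14/14 = 100% (76.8–100) | 6.7 | 13/14 = 92.9% | 0.5 |
| 13/15 = 86.7% (59.5–98.3) | 13/14 = 92.9% (66.1–99.8) | 6.2 | 12/14 = 85.7% | 1.0 |
| 12/15 = 80.0% (51.9–95.7) | 12/14 = 85.7% (57.2–98.2) | 5.7 | 11/14 = 78.6% | 1.4 |
| 17/18 = 94.4% (72.7–99.9) | 17/17 = 100% (80.5–100) | 5.6 | 16/17 = 94.1% | 0.3 |
| 16/18 = 88.9% (65.3–98.6) | 16/17 = 94.1% (71.3–99.9) | 5.2 | 15/17 = 88.2% | 0.7 |
| 15/18 = 83.3% (58.6–96.4) | 15/17 = 88.2% (63.6–98.5) | 4.9 | 14/17 = 82.4% | 1.0 |
| 19/20 = 95.0% (75.1–99.9) | 19/19 = 100% (82.4–100) | 5.0 | 18/19 = 94.7% | 0.3 |
| 18/20 = 90.0% (68.3–98.8) | 18/19 = 94.7% (74.0–99.9) | 4.7 | 17/19 = 89.5% | 0.5 |
| 17/20 = 85.0% (62.1–96.8) | 17/19 = 89.5% (66.9–98.7) | 4.5 | 16/19 = 84.2% | 0.8 |

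The ratio of gain to loss is x/(n−x). When most patients respond, an exclusion that happens to fall on a non-responder therefore moves the rate far more than one that falls on a responder.

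**Step 4. How easily a perfect score arises.** If the true rate were 90%, the chance that every treated patient responds is 0.9^15 = 20.6% for 15 patients and 0.9^20 = 12.2% for 20. Excluding the only non-responder produces the same headline.

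**The case against.** **Safeguards exist.** Set decisions come before lock and are minuted (SAP 3). PP and safety counts and major deviations are tabulated (SAP 4.2), deviations are listed (SAP 4.3), and all data, including crossmatch results, are listed (SAP 4.1, 4.4.2). With about 20 patients a careful reader could rebuild the all-treated rate. This stands, and it limits the harm. But lock is not blinding, a minute records a choice without making it independent of outcome, and the headline remains the PP rate.

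**No test is planned.** Protocol 12.2.1: "No formal statistical hypothesis testing will be performed in this study". This also stands: no error rate is affected. The descriptive proportion is then the whole primary result.

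**A reader might infer that the sponsor's pharmacokineticist controls the efficacy set**, because protocol 12.1 gives the PPS to the PK analyst and SAP 5 says of the PK analysis: "it will be performed by the Hansa Medical responsible pharmacokineticist". The documents do not support this. SAP 5 moves only the analysis of serum concentrations, the SAP drops the PK analyst's role in defining the set, and no protocol section assigns the crossmatch endpoint to the PPS. What remains is a difference between protocol and SAP that SAP 5 does not list.

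**A reader might infer that the SAP was written with the crossmatch results in hand.** Version 1.0, dated 13 July 2018, reports which time points are missing and that 3 patients had a second dose. That is missingness and a count, not results. Re-dosing is only a proxy for failure, since the SAP's response rule needs all recorded assays to be negative at 24 h.

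**A reader might infer that an outcome-driven exclusion has occurred.** The one documented exclusion (SAP 4.1) rests on an objective ground, a dose reduced for an allergic reaction. A closed list would remove the same patient. That patient's crossmatch outcome is not given, so the direction of its effect is unknown.

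**Conclusion.** The concern holds as a weakness of the plan, not as a shown bias. The only efficacy set depends on a grading that is undefined and is settled once outcomes are known at the sites, and the plan has no all-treated display to bound its effect.

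For one exclusion the possible shift is about +4.5 to +6.7 points if a non-responder is removed and about −0.3 to −1.4 points if a responder is removed. This rests on 15 to 20 treated patients and 1 to 3 non-responders, both assumed for illustration. The shift is modest beside the sampling uncertainty (for 18/20 the exact interval spans 98.8 − 68.3 = 30.5 points), but it can turn 14/15 or 19/20 into a perfect score. It should be corrected because the correction is cheap and protects the only primary estimate.

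**What to change.** 1. **SAP 3.2 and protocol 12.1.** Replace the undefined *major* with a closed list of PP exclusions: a named criterion from protocol 5.2 or 5.3 not met at dosing, or an actual dose that differs from the planned dose. Settle the list before the data review and apply it from a deviation listing without post-dose crossmatch, DSA or graft data. In protocol 12.1, delete the sentence that defers the criteria. Fixing the list before the first dose would have been better, but a SAP dated after dosing cannot meet that. Nor does a restricted listing hide everything, since second doses and missing crossmatches hint at outcome. Item 2 is therefore needed as well.
2. **SAP 4.4.1.** Present the primary endpoint for all treated patients with a positive pre-dose crossmatch, counting a missing 24 h result as non-response, with an exact 95% CI. Keep PP as supportive and state the crossmatch outcome of each excluded patient.
3. **Protocol 12.1 and SAP 5.** Limit the PK analyst's decision to a PK-evaluable set used for PK tables. Record the dropped FAS and the changed PP definition in SAP 5.

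**Cost.** A few sentences, one additional table and one restricted listing. The all-treated rate may be slightly lower than the PP rate, and an unforeseen type of deviation stays in PP and is described in the report.
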